4.1 Patient disposition

Patient disposition will be summarized by overall and will include:

- The number of patients screened
- Number of subjects screen failed
- Number of subjects enrolled
- Number of subjects in the Safety analysis set
- Number of subjects enrolled Period 1
- Number of subjects completed Period 1
- Number of subjects enrolled Period 2
- Number of subjects completed Period 2
- Number of subjects enrolled Period 3
- Number of subjects completed Period 3
- Total number of subjects having early termination all periods
- Reason Subject early termination (as per the CRF)

A patient level data listing of study completion information including the reason for premature study withdrawal, if applicable, will be presented.

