1.3 Study Objectives

The overall study objective is to assess the long-term safety and tolerability of simufilam.

This study has separate sets of objectives for the OL and RW phases. Safety and tolerability are the primary objectives of the OL phase. The primary objective of the RW phase is to assess patient response to blinded, randomized drug withdrawal.

Because drug safety in non-responders can be a critical component of a drug's risk-reward assessment, all patients who completed the 12-month OL phase were eligible to enter the RW phase, regardless of whether they previously showed an apparent response (or not) to open-label drug treatment.

Some study objectives overlap in the OL and RW phases. Hence, objectives are summarized separately below for the OL and RW phases, and for objectives spanning multiple phases. All objectives apply to mild-to-moderate Alzheimer's Disease (AD) patients, 50-85 years of age.

Objectives for the Open-label (OL) phase

- Assess the long-term safety and tolerability of OL treatment with simufilam 100 mg b.i.d. during 12-month repeat-dose oral administration.
- Assess mean changes from baseline on MMSE and compare those changes between patients with mild vs moderate AD.

Objectives for the Randomized Withdrawal (RW) phase

- Assess the safety and tolerability of treatment with simufilam 100 mg b.i.d. versus matching placebo over the 6-months study period.
- Assess patient response to blinded, randomized drug withdrawal on ADAS-Cog11.

Objectives Spanning Overall Study

Exploratory objectives tested across multiple phases are to:

- Characterize the safety and tolerability of simufilam during and up to 24 months of treatment.
- Assess mean changes from baseline on biomarkers and compare those changes between patients with mild vs moderate. For CSF biomarkers, change from baseline to M6 or M12 will be calculated. Plasma biomarkers will be analyzed for change from baseline to M6 and M12 for the OL phase and from M12 to M18 for the RW phase.

Note: All biomarker assessments in this study are exploratory endpoints that are not patient safety related, are 'Research Use Only' products, and, hence, are not intended to be compliant with FDA's Quality System Regulation (QSR) or ISO equivalent.

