Study data identified in the schedule of events are collected, and source verified, on the electronic data capture tool: Axiom Fusion eClinical Suite (Axiom, Toronto, ON, Canada).

All study data will be formulated into regulatory compliant data sets to provide transparency, traceability, and integrity of trial analysis results from the collection source. Observed study data will be mapped to the CDISC Study Data Tabulation Model (SDTM) and serve as the source data from the trial. All study analyses will be completed using analysis data sets that are derived from the SDTM and follow the CDISC Analysis Data Model (ADaM) architecture. All planned analyses will be performed using the ADaM data sets developed for this study.

The following Implementation Guides will be referenced for the configuration of SDTM and ADaM datasets:

- SDTM Model 1.7 and SDTM Implementation Guide (SDTM IG) version 3.3 will be used.
- ADaM Model 2.1 and ADaM Implementation Guide (ADaM IG) version 1.3 will be used.

Statistical Summaries

All statistical tests in all phases of the study will be two-sided and p-values of less than or equal to 0.05 will be considered statistically significant.

All p-values will be rounded and displayed in 3 decimal places. If a p-value less than 0.001 occurs, it will be shown in tables as <0.001.

Descriptive summaries of variables will be provided where appropriate. For continuous variables, the number of non-missing values (n) and the median, mean, standard deviation, minimum, and maximum will be tabulated by treatment. For categorical variables, the counts and proportions of each value will be tabulated by treatment.

Data will be presented as listings where applicable. Data not patient to analysis according to this plan will not appear in any tables or graphs but will be included in the data listings.

4 Analyses Spanning Overall Study

For the below analyses, it will be summarized by overall.

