4.7 Safety Analysis

Adverse Events

Treatment emergent AEs (TEAEs), defined as AEs that first occurred or worsened after first dose, will be summarized overall. Summary of TEAEs occuring in the Open-label phase (D1-M12 and M18-M24) will be summarized in one group . TEAEs occurring in Double-blind (RW) phase (M12-M18) will be summarized in other group. All the listings mentioned below to be provided for both the groups. The incidence of TEAEs will be reported as the number (percent) of patients with TEAEs within System Organ Class (SOC) and Preferred Term (PT). Patients will be counted only once within a SOC and PT, even if the patient experienced more than one TEAE within a specific SOC and PT. The number (percent) of patients with TEAEs will also be summarized by maximum severity and relationship. The denominators for calculating the percentages for summaries will be based on the number of patients in the analysis population enrolled to each group.

The following types of summary will be provided for Incidence of TEAEs:

- Treatment Emergent Adverse Events by System Organ Class and Preferred Term;
- Treatment Emergent Adverse Events by System Organ Class, Preferred Term and Maximum Severity;
- Treatment Emergent Adverse Events by System Organ Class, Preferred Term and Relationship to Study Drug;

The annualized incidence rate of AEs per person-years at risk, calculated as (365.25*number of AE occurrences)/(total treatment period with patients at risk of AE), will also be reported by most prevalent PT in the SOC.

The total period at risk for each patient will be defined as the period from first dose of study treatment to the date of the End of Treatment (EOT) (Month 12) or Early Termination (ET) visit for prematurely treatment discontinued patients. Annualized incidence rates will be expressed in terms of events per 100 patient years exposure.

Vital Signs

For Months 6, 12, 18, and 24, summary statistics will be provided (study population size, mean, SD, minimum, median, and maximum) for each vital sign parameter, by treatment group and overall. Summary statistics for change from baseline values will also be presented. Numbers and percentages of patients with abnormal values will be included.

ECG

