6.1 Efficacy Analysis

General Considerations

The FAS will be the primary data for efficacy analyses.

The primary efficacy estimand for the RW phase is

- Treatment regimen of interest: simufilam treatment for 6 months after OL treatment with simufilam for 12 months vs placebo treatment for 6 months after OL treatment with simufilam for 12 months
- Population:

As defined by inclusion / exclusion criteria

 Variable/Endpoint ADAS-Cog11 • Summary Measure

Difference between treatments in mean change from baseline (month 12) to endpoint (month 18, i.e. month 6 of RW Phase)

• Intercurrent events (ICE) strategy

The primary ICE of interest is early discontinuation of study drug, particularly for lack of efficacy. Given the RW phase is preceded by 12 months of OL treatment with simufilam, most patients entering the RW phase will have already demonstrated tolerability to simufilam; hence, discontinuations due adverse events are expected to be minimal. Discontinuations for lack of efficacy are likely given patients knowledge that the likelihood of being on placebo = 50%.

Discontinuations for lack of efficacy are consistent with a missing at random (MAR) mechanism and therefore a hypothetical strategy is relevant and meaningful. Therefore, a hypothetical strategy will be used to estimate the treatment effect as if the ICE if early discontinuation had not occurred.

Unless otherwise specified, for continuous endpoints that are scheduled to be assessed at > 1 postbaseline visit, mean changes from baseline will be analyzed using a restricted maximum likelihood (REML)-based repeated measures approach (MMRM). The MMRM analysis assumes an MAR mechanism. The analysis will include the categorical, fixed effects of treatment group and Visit, along with the continuous, fixed covariate of baseline value of the endpoint being analyzed (baseline), baseline MMSE score, and the interactions of treatment group, baseline, and baseline MMSE with Visit. An unstructured (co)variance structure will be used to model the within-patient errors. If this analysis fails to converge, the following structures will be tested in this order, with the first structure yielding convergence to be used as the appropriate structure for that variable: heterogeneous Toeplitz (TOEPH), heterogeneous compound symmetric (CSH), and compound symmetric (CS). The Kenward-Roger approximation will be used to estimate denominator degrees of freedom.

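### SAP v3.0 specifies no summary table of randomized-withdrawal discontinuation, its reasons, or adverse events by randomized arm

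*SAP*

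**What the plan says.** The lead-in to SAP Section 4, which covers 4.1 to 4.7, says "For the below analyses, it will be summarized by overall". SAP 4.1 repeats this for disposition: "Patient disposition will be summarized by overall and will include" a list of counts. For the RW phase the list has enrolled and completed counts only, for example "Number of subjects completed Period 2". It then gives "Total number of subjects having early termination all periods" and one line headed "Reason Subject early termination (as per the CRF". None of these lines mentions randomized arm, and the last two are not split by period. SAP 4.1 also plans a patient-level listing of completion status with the reason for withdrawal.

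SAP 4.7 forms two TEAE groups by phase: the two open-label periods together, and the RW phase as the other. It lists three tables: by system organ class and preferred term, "Treatment Emergent Adverse Events by System Organ Class, Preferred Term and Maximum Severity", and by relationship to drug. In the same section, vital signs, ECG and laboratory data are to be shown both by treatment group and pooled.

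Two other sections depend on RW discontinuation and tolerability by arm. SAP 1.3 lists as an RW objective: "Assess the safety and tolerability of treatment with simufilam 100 mg b.i.d. versus matching placebo over the 6-months study period". SAP 6.1 names early discontinuation of study drug as the main intercurrent event. It supports the hypothetical strategy by saying that "discontinuations due adverse events are expected to be minimal" and that stopping for lack of efficacy is likely because patients know they have an even chance of receiving placebo.

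**The concern.** A safety and tolerability objective worded as a comparison with placebo needs adverse events and discontinuations shown for each arm. As written, SAP 4.7 merges simufilam and placebo patients in the RW adverse event tables, and SAP 4.1 merges them in the disposition table.

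The choice of estimand also rests on two descriptive expectations about the RW phase: few discontinuations for adverse events, and a fair number for lack of efficacy. Whether they held can be seen only from RW reasons, and whether they held alike in both arms only from RW reasons by arm. The planned reasons line mixes RW terminations with those from the open-label periods. A clinical study report built exactly to this SAP could therefore present the RW result without a summary of who stopped, when, why, and on which arm.

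**Working it through.** The plan states no RW dropout rate and no number randomized, so there is no figure to reproduce. The check compares the text and adds an illustration of what the pooled display can hide.

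**Text comparison (SAP v3.0)**

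| Output | Grouping stated | RW shown by arm? |
|---|---|---|
| Period 2 enrolled, completed (4.1) | Overall | No |
| Early termination total (4.1) | Overall, all periods | No |
| Termination reasons (4.1) | Overall, not split by period | No |
| Completion listing with reason (4.1) | Per patient | Arm not named as a column |
| Three TEAE tables (4.7) | By phase, RW as one group | Not stated |
| Serious events, deaths, events leading to discontinuation (4.7) | Not in the list | No |
| Vital signs, ECG, laboratory (4.7) | By treatment group and pooled | Yes, reading treatment group as RW arm |

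The last row matters because, where the authors wanted a split by arm inside Section 4, they wrote it. Disposition and TEAEs do not carry that wording.

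**Inputs for the illustration.** Enrolled 220, open-label dropouts 43, not continuing 21 (20 + 1), all from SAP 2.5. Allocation is 1:1 (SAP 2.2). RW dropout is assumed.

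**RW entrants.** 220 − 43 − 21 = 156 at most, and 156 / 2 = 78 per arm.

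**What the Period 2 line can hide.** Assume 20 RW dropouts, so the planned line shows 20/156 = 12.8% not completing:

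| Split between arms | Per cent of 78 | Fisher exact p |
|---|---|---|
| 10 vs 10 | 12.8 vs 12.8 | 1.00 |
| 8 vs 12 | 10.3 vs 15.4 | 0.47 |
| 7 vs 13 | 9.0 vs 16.7 | 0.23 |
| 6 vs 14 | 7.7 vs 17.9 | 0.09 |
| 5 vs 15 | 6.4 vs 19.2 | 0.03 |

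All five rows give the same planned summary. The p-values only describe how far apart the arms could be; none is a forecast.

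**What the reasons line can hide.** RW cases are pooled with the 43 open-label dropouts. With D RW dropouts and none in Period 3, the RW share is D/(43 + D):
- D = 8 (5% of 156): 8/51 = 16%
- D = 20: 20/63 = 32%
- D = 31 (20% of 156): 31/74 = 42%

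With 10 Period 3 dropouts (assumed), the shares for D = 8 and D = 31 fall to 8/61 = 13% and 31/84 = 37%. Across this range most of the reasons shown would come from outside the RW phase.

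**The case against.** The strongest reply is that the information is not lost. SAP 4.1 plans a patient-level listing with withdrawal reasons, and SAP 3.2 puts all eCRF data in listings. Total RW non-completion follows from the Period 2 counts. The numbers of patients in the by-arm vital signs and laboratory tables at Months 12 and 18 give a rough view of retention by arm. Withdrawals for adverse events are recorded as such on the eCRF (Protocol 9.1) and would be counted in the reasons line. All of this stands. A reader might infer that RW dropout by arm will never be visible, and the documents do not support that. What remains is narrower: a listing is not a summary, arm is not named as a column in it, and visit counts give no reasons.

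Second, SAP 3.2 has a general rule that categorical variables are tabulated by treatment, and Section 4 does split some outputs by arm. So the pooled wording may not be meant to exclude arms. That is fair. The general rule and the specific wording conflict, and the text does not say which prevails. This is a reason to reconcile them.

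Third, it is tempting to say that by-arm dropout would show whether the missing-at-random assumption holds. It would not: unequal dropout can be missing at random, and equal dropout can fail to be. The table can only describe whether the two expectations in SAP 6.1 were met.

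Fourth, SAP 1.2 says versions 1.0 and 2.0 were used for the open-label and RW analyses. They are not available here and may have contained such tables. The point therefore covers version 3.0 only, which SAP 1.2 assigns to the final data and the clinical study report.

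**Conclusion.** The point holds as a gap in the specified outputs. SAP v3.0 has no summary table of RW discontinuation, its reasons, or adverse events by randomized arm, and no table of serious events, deaths or events leading to discontinuation. It does have an RW objective against placebo and an estimand built around drug discontinuation. No estimate or test changes, and the primary RW model is unaffected.

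The size cannot be fixed from the documents, because they give no RW dropout rate. The illustration rests on three assumptions: that all 156 remaining patients entered RW, that allocation gave 78 per arm, and that 20 dropped out. A reader might take the 5 vs 15 split as evidence of differential dropout. It is only one of the splits that fit the same pooled line, and 10 vs 10 fits equally well. The change is worth making because the objective asks for the comparison and the data are already collected.

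**What to change.** - **SAP 4.1.** For Period 2, replace the overall summary with a table by randomized arm: randomized, dosed, completed, and discontinued by reason and by last visit attended (Month 12 or Withdrawal Day 1, Month 13, Month 15). The first category is needed for patients who leave before Month 13. Separate stopping study drug from leaving the study: the intercurrent event in 6.1 is the former, the 4.1 list counts the latter, and Protocol Section 8 treats them as distinct choices.
- **SAP 4.7.** Present all RW-phase TEAE tables by arm. Add serious events (including deaths) and TEAEs leading to discontinuation, by phase and, for RW, by arm.
- **SAP 6.1.** State that the Period 2 table describes whether the two expectations about discontinuation held, and that it is not a test of the missing-at-random assumption.
- **SAP 3.2 and Section 4.** Reconcile the general by-treatment rule with the overall wording, so that it is clear which outputs are split by arm.

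Cost: a few descriptive tables. Discontinuation reasons and adverse event withdrawals are already required to be recorded (Protocol Section 8 and 9.1), so no new data are needed.

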4.2 Protocol Deviations

All protocol violations will be captured directly in Fusion and will be presented in a data listing.

4.3 Demographics and Baseline Characteristics

The demographics consist of age (year), sex, race, and ethnicity. The baseline characteristics consist of baseline height (cm), baseline weight (kg), and baseline body mass index (BMI) (kg/m²). Body mass index is calculated as (body weight in kilograms) / (height in meters)².

Patient demographic data and baseline characteristics will be summarized descriptively overall. The demographic data and baseline characteristics will be summarized based on the safety population.

4.4 Medical History

Medical history will be coded using Medical Dictionary for Regulatory Activities (MedDRA).

Patient medical history data including specific details will be presented in a listing.

4.5 Concomitant Medications

All medication data will be presented in listings. The number (%) of patients taking AD symptomatic medication at baseline (day 1) and throughout the study will be summarized.

Version 3.0 CONFIDENTIAL, MATERIAL NON-PUBLIC INFORMATION Page 13 of 19

4.6 Treatment Compliance and Extent of Exposure

Study medication compliance will be calculated based on the numbers of tablets dispensed minus the number of tablets returned divided by the expected number of tablets based on the duration of the patient's participation in the study and will be summarized as continuous and categorical variables. Compliance will be summarized as a continuous outcome using mean, SD, median, min, and max. For the categorical analysis, a patient will be considered compliant if the amount of medication taken is within the range of 75% - 125% of the amount of medication planned to be taken.

Total number of days the patient is on study drug will be summarized as a continuous variable. The Days a patient is on study drug will be calculated as the number of days from date of first dose to date of last dose plus 1.

Treatment compliance will be summarized overall.

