7.2.8. Month 12 and 24 Follow-up Visits

Patients will return to clinic in the morning before taking their morning dose. Patients who were enrolled prior to this amendment can terminate after completing the original 12-month open-label portion or can reconsent to the randomized withdrawal and final 6-month open-label portion. Month 12 morning dose in the clinic will be from Open-Label Period 1 bottle. Month 12 evening dose will be from the Randomized Period 2 bottle.

Within 30 min prior to dosing, the following assessments will be conducted:

- Clinical laboratory tests (blood and urine)
- Plasma sample collection (from 8 mL whole blood) for SavaDx and other plasma biomarkers.

After dose, the following assessments will be conducted:

- Full physical exam
- Adverse event monitoring
- MMSE-2
- ECG
- ADAS-Cog11, NPI, GDS, and C-SSRS Since Last Visit version. If the C-SSRS indicates imminent risk for suicidality, defined as the patient positively endorsing questions 4 or 5 of the suicidal ideation section or any suicidal behavior questions, discontinue study drug and refer for appropriate care.
- CSF sample collection at Month 12 (time post-dose to be recorded) for patients with a screening CSF who did not provide a CSF sample at Month 6. For those patients who provided a Month 6 CSF, this Month 12 CSF will be OPTIONAL. After 50 patients have provided either Month 6

or Month 12 CSF, no additional patients will have CSF drawn after screening. No CSF will be drawn at Month 24.

For patients undergoing a CSF draw, CSF sample collection (5 mL) will occur 1-3 h after dosing and after the MMSE, ADAS-Cog11, NPI and GDS testing has been completed. These samples will be tested for CSF biomarkers.

Patients who complete Month 12 prior to availability of drug supply for the randomized withdrawal phase (Months 12 - 18) will be dispensed additional openlabel simufilam and will return for a Withdrawal Day 1 Visit as appropriate.

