3.2 General Considerations that Apply to All Phases

Analysis Populations

Three analysis sets are defined for each phase of the study.

- The Full Analysis Set (FAS) includes all patients who receive at least one dose of study treatment and have evaluable efficacy records at baseline and post-baseline visits.
- The Per Protocol Analysis Set (PP) is the same as the FAS minus patients with major violations of protocol inclusion or exclusion criteria, e.g., other or interfering neurologic disorders such as posterior cortical atrophy, frontotemporal dementia, multiple psychiatric diagnoses, taking anxiolytics, or significant history of cardiovascular disease. PP also excludes patients who refused assessments for one or more visits and patients who were < 65% compliant by pill counts.
- The Safety analysis set will include all patients who receive at least one dose of the study treatment. All safety analyses will be based on the Safety population. Patients will be analyzed as treated.

Defining Mild vs Moderate Baseline Severity

For the purposes of analyses in all phases of the study, mild AD is defined as baseline MMSE \geq 21, and moderate AD as baseline MMSE \leq 20.

Management of Analysis Data

All tables, listings and figures will be presented in landscape format. All outputs will be sent to CSI as electronic files in Rich Text Format (RTF) format documents.

Definition of Analysis Timepoints

Scheduled analysis visits are visits upon scheduled time points as specified in Table 1 Schedule of Time and Events.

Scheduled analysis visits during the study period will be windowed to the nearest scheduled visit within the same phase.

Unscheduled visits are visits with data not collected at scheduled time points. Unscheduled visits will be windowed to the nearest scheduled visit as described above.

For the purposes of calculating change from baseline in the tables, if there is an unscheduled visit with a value and the visit BEFORE the unscheduled visit (i.e., scheduled visit) does not have a value for that assessment, the value associated with unscheduled visit can be used. Else, disregard the unscheduled visit, if scheduled visit is available and has a value.

There will be one valid value of assessment kept for each scheduled analysis visit in summary / analysis statistics. All unscheduled visits will be included as collected in eCRF in listings.

Handling of Missing Data and Partial Dates

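### SAP 4.6 pools pill-count compliance over the whole study, so it cannot show or compare by arm the intake of randomized-withdrawal tablets, and the 65% per-protocol cut names no period or formula

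*SAP*

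**What the plan says.** SAP 4.6 takes the "numbers of tablets dispensed minus the number of tablets returned" and divides by the "expected number of tablets based on the duration of the patient's participation in the study". A patient counts as compliant if intake is "within the range of 75% - 125% of the amount of medication planned to be taken". On the level of reporting it says only: "Treatment compliance will be summarized overall". No other pill-count formula appears in the SAP.

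SAP 3.2 states: "Three analysis sets are defined for each phase of the study". The FAS "includes all patients who receive at least one dose of study treatment and have evaluable efficacy records at baseline and post-baseline visits". The PP set is the FAS less certain exclusions, one of which is "patients who were < 65% compliant by pill counts". That rule names no period and does not refer to 4.6.

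SAP 2.2 sets out 12 months of open-label treatment, 6 months of RW (simufilam or placebo, 1:1) and 6 further open-label months, with twice-daily dosing throughout. SAP 6.1 makes the FAS primary for RW efficacy. Sections 5 to 7 assign no analysis to PP.

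**The concern.** The RW contrast compares simufilam with placebo taken in Months 12 to 18. A simufilam-arm patient who stops the RW tablets but stays in the study is in effect withdrawn, which pulls the arms together. Reading a small or null RW difference therefore requires knowing how much randomized drug was taken in each arm.

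A compliance figure pooled over the whole study cannot show this, because three quarters of its weight for a completer comes from open-label drug. It is also not split by arm, although SAP 4.7 reports vital signs, ECG and laboratory data by treatment group as well as overall. The exposure measure in 4.6 does not fill the gap: it counts days from first to last dose, so a patient who skipped the RW tablets and resumed at Month 18 shows no interruption. If the same pooled figure is used for the 65% rule, the RW PP set would also fail to screen out patients who barely took RW drug.

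**Working it through.** The plan reports no compliance value to reproduce, so the check applies the 4.6 ratio to the planned durations.

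**Inputs.** Open-label 12 months, RW 6, open-label follow-up 6 (SAP 2.2). Dosing is twice daily throughout, so the daily tablet count cancels and months serve as weights. Cut-offs: 75% to 125% compliant (SAP 4.6, lower bound read as inclusive) and below 65% excluded from PP (SAP 3.2). Let a be the fraction of open-label tablets taken and r the fraction of RW tablets taken. The values of a are illustrative.

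**Month 24 completer.** Score = (12a + 6r + 6a)/24 = 0.75a + 0.25r.

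| a | score at r = 0 | r needed to reach 75% | r below which score < 65% |
|---|---|---|---|
| 100% | 75.0% | 0% | -40% (impossible) |
| 95% | 71.3% | 15% | -25% (impossible) |
| 90% | 67.5% | 30% | -10% (impossible) |

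The third column is (0.75 - 0.75a)/0.25 and the fourth is (0.65 - 0.75a)/0.25. With r = 0 the score falls below 65% only if a < 0.65/0.75 = 86.7%. With a = 100% and r = 50% the score is 0.75 + 0.125 = 87.5%.

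**Leaving during or at the end of RW, a = 100%, r = 0.** Score = 12/(months in study): Month 13, 12/13 = 92.3%; Month 15, 12/15 = 80.0%; Month 18, 12/18 = 66.7%. The first two count as compliant and none is below 65%. For a Month 18 leaver in general the score is (12a + 6r)/18, and here the 65% rule can bite: at a = 95% when r < (11.7 - 11.4)/6 = 5%, and at a = 90% when r < (11.7 - 10.8)/6 = 15%.

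**Sensitivity.** The 5-day visit window (Protocol 7.2.3), applied at both ends of the RW phase, moves the 75.0% to between 73.6% and 76.4%. Some patients stayed on open-label drug while waiting for RW supply. The documents give no waiting time; assuming 1, 2 or 3 months, 75.0% becomes 19/25 = 76.0%, 20/26 = 76.9% or 21/27 = 77.8%.

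**Restricted to the RW phase.** The same patients score r itself: 0% with no tablets and 50% with half. Both are below 65%.

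**The case against.** Several points against the concern have force.

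- A reader might infer that a patient who took none of the RW tablets stays in the RW PP set. The documents do not establish this. The sets are phase-specific and PP is a subset of the FAS. If the one-dose condition means a dose in that phase, such a patient is outside the RW FAS and hence outside PP, whatever the score. The SAP leaves this open. The supportable case is a patient who took almost none: one tablet meets the condition on either reading and barely moves the score.
- The 65% rule does not cite 4.6, and phase-specific sets may imply a phase-specific count. That stands, but no such count is defined, so the rule still needs wording.
- It would be too broad to say that neither cut-off works. A completer with r = 0 reaches the 75% bound only with essentially perfect open-label intake; at a = 99% the score is 74.3%, which is not compliant. The 75% cut therefore flags most such completers. It misses those who leave early in RW and many with partial RW intake.
- PP feeds no specified analysis, so no planned estimate or test changes. This stands and limits the severity.
- Other information exists. SAP 4.1 reports Period 2 enrolment and completion, and SAP 6.1 handles early discontinuation of study drug as an intercurrent event. Neither measures intake among patients who stay on study. The protocol takes pre-dose PK samples at Months 15 and 18, but the SAP plans no PK analysis and its Table 1 has no PK row.
- Section 4 covers the whole study, so an overall summary there is deliberate. No phase-specific summary is given elsewhere.

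**Conclusion.** The concern holds in a limited form. The only compliance formula pools all periods and both arms. It cannot show RW intake or compare it between simufilam and placebo. For a Month 24 completer with open-label intake of 90% to 100%, near-zero RW intake scores 67.5% to 75.0%, and no level of RW intake brings the score below 65%. Whether this affects the RW PP set depends on two things the SAP does not state: whether the 65% rule uses the 4.6 figure, and whether the FAS one-dose condition is phase-specific.

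The consequence is confined to the compliance output and the PP set. A reader might conclude that the primary RW comparison is itself compromised. The documents do not support that: it uses the FAS, and compliance does not enter the model. What is lost is the means, within the planned compliance output, to judge whether poor adherence contributed to a small or null RW difference. The figures assume constant intake within open-label and RW periods and nominal durations, except where a range is shown.

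**What to change.** In SAP 4.6, compute compliance separately for Periods 1, 2 and 3: tablets used in that period (dispensed less returned) over tablets expected in that period. Summarize Period 2 by randomized arm, using the existing continuous and categorical formats. Count open-label tablets taken while waiting for RW supply in Period 1.

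In SAP 3.2, state that each phase's 65% exclusion uses that phase's compliance, and that the FAS one-dose condition refers to a dose in that phase.

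The cost is SAP wording and one more table. SAP 4.1 already reports disposition by period, and RW drug is identifiable from its own supply (Protocol 7.2.8: "Month 12 evening dose will be from the Randomized Period 2 bottle"). The documents name Period 1 and Period 2 bottles only, so Period 3 counts may have to rely on dispensing records from Month 18. The RW PP set may shrink slightly. SAP 1.2 says earlier SAP versions were used for the open-label and RW analyses; if the final data are already locked, the Period 2 table can be added as a clearly identified post-hoc analysis, which SAP 1.1 allows.
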